5 PROCEDURES

5.1 Study procedures. Using lay language, provide a complete description of the study procedures, including the sequence, intervention or manipulation (if any), drug dosing information (if any), use of records, time required, and setting/location. If it is available and you think it would be helpful to the IRB: Upload a study flow sheet or table to the **Supporting Documents** SmartForm in **Zipline**.

For studies comparing standards of care: It is important to accurately identify the research procedures. See UW IRB [POLICY: Risks of Harm from Standard Care](#) and the draft guidance from the federal Office of Human Research Protections, ["Guidance on Disclosing Reasonably Foreseeable Risks in Research Evaluating Standards of Care"](#); October 20, 2014.

This research study will be conducted in addition to standard of care procedures for PrEP use. Therefore, clinical procedures, including blood draws for laboratory testing, STI screening, PrEP prescriptions, and adherence counseling will be performed in accordance with the clinic's standard of care. Participants will be followed in this study and have visits at entry (baseline), and then at months 1, 3 and 6.

The research procedures, in addition to informed consent, that all participants will get in addition to the standard of care, are the following:

- Randomization: After consent has been obtained the clinical site will send documentation of eligibility (checklist) and the signed informed consent, HIPAA authorization, and ROI to the study team at UW. The site will either email the documents or provide them in person to a study team member. Once these documents are received, the research coordinator will send the participant a link to the baseline survey. After completion of the baseline survey, the participant will be randomized to one of the two intervention groups: standard of care, or peer navigation. The research coordinator will open a sequentially numbered, sealed envelope with the study allocation (generated by site using blocked randomization with variable block sizes and random number generator). They will record the treatment assignment of the participant in their de-identified chart and send a text or email to inform the participant of their assignment.

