- Surveys: Participants will be asked to complete an online survey at the entry visit (baseline) and at 3 and 6 months. They will be sent a unique link to the survey by text and reminders if they do not complete it. If a participant does not complete their baseline survey within 7 days they will be replaced in the study. Extenuating circumstances (such as sudden job loss, health emergencies and legal issues for robberies) can be made to extend this baseline survey deadline within a reasonable timeframe at the discretion of the PI.

- Fingerstick for dried blood spots: At all follow-up visits (1 month, 3 months, and 6 months) we will collect a blood specimen via fingerstick and use it to obtain dried blood spots, which will be used to test for the presence of the medications in PrEP (tenofovir and emtricitabine).
- Intervention groups:
 - Standard of care: The up to 20 participants who are assigned to the standard of care, will only be asked to participate in the research procedures described above.
 - Peer navigation: For the up to 20 participants who are assigned to the peer navigation group, they will receive peer support. These activities include, but are not limited to, in-person meetings, appointment reminders and escort, refill assistance, and check-ins about adherence. The activities that the participant receives will be in response to their needs and requests. The peer will introduce themselves to participants in this intervention arm within 2 business days of when the participant completes the survey, via their preferred method of contact (as recorded at the clinic during the entry visit). The peer will schedule their first in-person meeting within 1 week of enrollment. As some meth users will have greater functioning than others, the peer will create an individualized plan for each subject and tailor activities and resources based on acuity. Individualized plans will be completed at study enrollment and exit to be able to record needs and progress during the study. Additional individualized plans may be completed during follow-up at the discretion of the peer and depending on the needs and acuity of the participant.

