¹ The research procedures of the enrollment visit may be performed on the same day of the initial PrEP clinical visit, or on the following day.

New activities for all MSM/TGP participants and PrEP providers:

The research coordinator will conduct semi-structured interviews with all willing study MSM/TGP participants and PrEP provider (prescribers, caseworkers, peer educators, and PrEP navigators) participants to better understand the challenges and barriers to PrEP initiation and engagement in the PrEP care continuum. Interviews will be digitally audio-recorded and transcribed verbatim, and identifying information will be deleted. The information sheet and interview guide for these interviews have been uploaded to Zipline. Interviews can be conducted in-person, by phone, or by Zoom videoconference.

Note: Remote interviews will be preferred, however an in-person option is being made available due to potential access issues. It is anticipated that most (if not all) will be remote. Attention will be paid to COVID safety protocols and guidelines including symptom screening if an interview is done in-person.

5.2 Data variables. Describe the specific data you will obtain (including a description of the most sensitive items). If you would prefer, you may upload a list of the data variables to the **Supporting Documents** SmartForm instead of describing the variables below.

We will obtain contact information from the clinic at enrollment and all participants will complete an ROI so we can obtain their clinical information related to PrEP. We will also obtain drug level testing results (tenofovir and emtricitabine) once the study is over.

The data we will obtain from the baseline and follow-up surveys are uploaded in Supporting Documents.

The peer will complete individualized plans for each participant assigned to peer navigation. The peer will also complete a contact log with all of the participant contacts they have that are not already recorded in the text platform, individualized plans, or the peer's cell phone. Examples of the individualized plan and contact log have been uploaded in the Supporting Documents SmartForm.

We will obtain interview data from participants who consent to participate in an end-of-study interview. An interview guide has been uploaded in the Supporting Documents SmartForm with interview questions.

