5.3 Data sources. For all types of data that you will access or collect for this research: Identify whether you are obtaining the data from the subjects (or subjects' specimens) or whether you are obtaining the data from some other source (and identify the source).

If you have already provided this information in Question 5.1, you do not need to repeat the information here.

We are obtaining the data from the subject (contact information, self-reported survey data, dried blood spots, reported behavior and PrEP adherence, etc.). We will also obtain PrEP pharmacy refill data as available. We will also collect data recorded by the peer (individualized plan, contact log), and data recorded on the text platform (number of texts, content, etc.). Correspondence between the peer and the participants assigned to the peer navigation group will also be considered study data. We will count the frequency of contacts of different types (e.g., text, call, in-person) and describe the contact (e.g., call to pharmacy to help with refills).

5.4 Retrospective/prospective. For all types of data and specimens that you will access or collect for this research: do all data and specimens to be used in the research exist (for example, in subjects' medical records) at the time this application is being submitted for initial review?

	No
	Yes

Include any necessary comments or explanation below (Note that for most studies this can be left blank):

5.5 Identifiability of data and specimens. Answer these questions carefully and completely. This will allow HSD to accurately determine the type of review that is required and to assist you in identifying relevant compliance requirements. Review the following definitions before answering the questions:

Access means to view or perceive data, but not to possess or record it. See, in contrast, the definition of "obtain".

Identifiable means that the identity of an individual is or may be readily (1) ascertained by the researcher or any other member of the study team from specific data variables or from a combination of data variables, or (2) associated with the information.

Direct identifiers are direct links between a subject and data/specimens. Examples include (but are not limited to): name, date of birth, medical record number, email or IP address, pathology or surgery accession number, student number, or a collection of your data that is (when taken together) identifiable.

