In order to obtain consent, the clinical/study staff will meet with an interested and eligible participant in a private setting and review the UW HSD-approved consent form with them. If the staff has a time conflict or are at a site outside of Gay City or Kelley-Ross the clinic staff will reach out to the UW study team (Principal Investigator, Study Coordinator and/or Peer Navigator) to provide consent. In these cases one of the UW study team members will consent the individual within 7 days at either at the study site or in another private location at UW or with a community partner (e.g., a private room at Gay City). All personnel who perform consent will ensure that the participant knows that participating in research is voluntary and that they can stop their participation at any time. Specifically, the clinical/study staff will inform the individual that they can receive PrEP at the clinic without participating in the study, if they would prefer not to participate. Once the consent is reviewed, all questions have been answered, and the staff is confident the client understands the procedures, the client and the staff will both sign and date the consent form.

The Gay City PrEP clinic also offers PrEP visits by telemedicine for people who cannot come to the Wellness Center during the weekly clinic hours and at outreach settings where Gay City offers HIV testing, including UTOPIA in Kent, WA. Telemedicine visits are only done for the initial PrEP visit for clients; for follow-up PrEP visits the HIV tester will see the client without the provider's presence via telemedicine. During the initial visit the HIV tester is with the client in-person and uses a HIPAA-compliant telemedicine platform (Zoom) through their UW Net ID account to connect with the provider. Together, the tester and provider conduct the visit, including informing the client about PrEP, assessing for eligibility, and determining next steps (e.g., how to help client with insurance/financial assistance for PrEP; if behaviorally eligible, provider will prescribe PrEP once eligibility is confirmed after reviewing lab results). The tester performs any specimen collection, weight measurements, etc. The tester and provider are in private settings during telemedicine appointments to ensure the privacy of the client.

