d. Influence. Does your research involve any subject groups that might find it difficult to say "no" to your research because of the setting or their relationship with you, even if you don't pressure them to participate?

Examples: Student participants being recruited into their teacher's research; patients being recruited into their healthcare provider's research, study team members who are participants; outpatients recruited from an outpatient surgery waiting room just prior to their surgery.

	No
	Yes

→ If yes, describe what you will do, for each of these subject groups, to reduce any effect of the setting or relationship on their decision.

Examples: a study coordinator will obtain consent instead of the subjects' physician; the researcher will not know which subjects agreed to participate; subjects will have two days to decide after hearing about the study.

The lead researcher is also the prescribing physician at the Gay City Health Project. If she has a potential client who is eligible to participate, she will inform them of the study and emphasize that they can continue to get PrEP at Gay City without participating if that is their preference. The Gay City PrEP clinic is not a primary care clinic, but instead is a safety net clinic that follows people who initiate PrEP until they can be linked to a primary care provider for continued use (typically up to a few months) and assists with this linkage. So the PI is not the primary care provider for the Gay City PrEP clients. All clients who decide not to initiate PrEP are provided information on other locations to get it if they so choose to in the future.

e. Ongoing process. For research that involves multiple or continued interaction with subjects over time, describe the opportunities (if any) you will give subjects to ask questions or to change their minds about participating.

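### Does letting the Peer Navigator take consent before randomization contaminate the control arm or blur the measures of peer contact?

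*Protocol*

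**What the plan says.** Section 8.2.b gives consent to clinical or study staff in the first instance. Where staff have a time conflict, or the site is not one of the two original clinics, "clinic staff will reach out to the UW study team (Principal Investigator, Study Coordinator and/or Peer Navigator) to provide consent". One member of that team then sees the person within 7 days in a private place. The meeting consists of reviewing the approved form and answering questions, after which participant and staff member both sign and date it.

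Section 5.1 fixes what follows. The signed consent goes to the study team and the baseline survey link is sent out. Then: "After completion of the baseline survey, the participant will be randomized to one of the two intervention groups". "The research coordinator will open a sequentially numbered, sealed envelope with the study allocation".

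Under the peer navigation arm, the same section says "The peer will introduce themselves to participants in this intervention arm within 2 business days" of survey completion, and "The peer will schedule their first in-person meeting within 1 week of enrollment". Section 5.2 adds: "The peer will also complete a contact log with all of the participant contacts they have" (those not already recorded elsewhere). Section 5.3 adds: "We will count the frequency of contacts of different types (e.g., text, call, in-person) and describe the contact".

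**The concern.** The peer is the intervention. If the peer takes consent before the arm is known, two things seem to go wrong.

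- A person later assigned to standard of care, who is meant to receive research procedures only, has already met the intervention provider in private. That might dilute the contrast between arms.
- A person later assigned to peer navigation has already met the peer, so the introduction and first in-person meeting in section 5.1 are no longer first encounters. If the consent meeting entered the contact log, the count of in-person contacts would depend on who happened to take consent. Prior familiarity might also colour answers on acceptability.

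The trial is a pilot of acceptability and feasibility (section 1.5), and sections 5.5.c and 9.6.b name quantity and frequency of peer correspondence as relevant to the aims. The route need not be rare either: section 3.1 opens recruitment to any King County PrEP provider, because few eligible people were seen at the two original sites.

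**Working it through.** **Order of events.** Consent, documents to the study team, baseline survey, then randomization (sections 8.2.b and 5.1). The order is as the concern describes it: whoever takes consent does not know the arm.

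**What the exposure is.** Section 5.1 illustrates peer support with in-person meetings, appointment reminders and escort, refill help and adherence check-ins. A consent review is not among the examples, and section 8.2.b confines it to the form and the person's questions. A future control who is consented by the peer therefore receives a research procedure and no navigation. Section 5.11, which rules out additional contact with the standard of care group, concerns people already enrolled and assigned, so it is not breached.

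**Whether section 5.1 is contradicted.** The introduction and the first in-person meeting stand under the peer navigation arm and follow assignment. They describe the opening of the intervention. They do not claim that the two people have never met.

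**How many people could be affected.** The protocol gives no figure. Assume the peer consents k of 40 participants, 20 per arm (the maxima in section 2.7), with every set of k equally likely.

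- Expected number per arm: k/2.
- P(at least one control met the peer) = 1 − C(20,k)/C(40,k).

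| k | Expected per arm | P(at least one control met the peer) |
|---|---|---|
| 0 | 0 | 0 |
| 1 | 0.5 | 1 − 20/40 = 0.500 |
| 2 | 1 | 1 − 190/780 = 0.756 |
| 4 | 2 | 1 − 4,845/91,390 = 0.947 |

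Blocking by site would alter these values somewhat, which does not affect the argument. The probability climbs quickly because it asks only whether one of 20 controls ever met the peer. It says nothing about any effect on an outcome. The expected number is the same in both arms.

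**Effect on the contact count.** If every consent meeting were logged as a navigation contact, the peer-arm mean would rise by (k/2)/20 = k/40 on average: 0.10 at k = 4 and 0.50 at k = 20. The text does not point to that reading:

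- The contact log in section 5.2 follows a sentence on participants assigned to peer navigation.
- The counting sentence in section 5.3 follows one on correspondence with that same group.
- Section 5.3 also has each contact described, so a logged consent meeting could be told apart from a navigation contact.
- Time to first in-person meeting is not named as a study measure. The one-week target in section 5.1 is a delivery step.

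**Whether the consenter can be identified.** Yes. The staff member signs the consent form and the study team receives it.

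**The case for a change.** The best case for the concern is that it needs no proof of contamination. Read literally, a log of all the peer's participant contacts takes in a consent meeting, and no sentence excludes it. Two other roles could take consent, so removing the peer would need only a few words and no new staff. Recruitment beyond the two original clinics makes the fallback route a regular one.

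Part of this stands. The protocol does not say in terms whether a consent meeting counts, and the route may well be used. But the missing rule is a detail that an analyst would settle sensibly from the context of sections 5.2 and 5.3. The log form was uploaded separately and is not at hand, and such a rule could equally sit there or in an analysis plan.

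Nor is removing the peer plainly better. It cuts the fallback consenters from three to two, within a 7-day window, in a study short of eligible people. It also moves consents to one of two people with conflicts of their own:

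- The Principal Investigator: "The lead researcher is also the prescribing physician at the Gay City Health Project", a relationship that section 8.2.d itself treats as a possible influence on consent.
- The coordinator, who opens the allocation envelopes and conducts the end-of-study interviews on acceptability (section 5.1). This takes the study coordinator of section 8.2.b to be the research coordinator named elsewhere. If familiarity with the consenter colours such answers, the change could move that problem to the interviewer.

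**Conclusion.** The concern does not hold. The protocol misstates and contradicts nothing here: the peer may take consent, and navigation starts after assignment. The exposure is a consent review, it precedes assignment, and it is balanced across arms in expectation. Allocation concealment is untouched, because the coordinator opens sealed, numbered envelopes after the baseline survey.

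The number of people affected cannot be derived and may be zero. No figure in the protocol links one consent conversation to a later outcome. The only calculable effect is a rise of k/40 in the mean number of in-person contacts, and it arises only if consent meetings are logged as navigation, which the context of sections 5.2 and 5.3 does not suggest. This conclusion assumes that the peer keeps to the consent review that section 8.2.b describes. Who takes consent is a defensible staffing choice in a small pilot. A sentence saying that consent meetings are not navigation contacts would be harmless, but the plan is not deficient without it.

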9 PRIVACY AND CONFIDENTIALITY

9.1 Privacy protections. Describe the steps you will take, if any, to address possible privacy concerns of subjects and potential subjects.

Privacy refers to the sense of being in control of access that others have to ourselves. This can be an issue with respect to recruiting, consenting, sensitivity of the data being collected, and the method of data collection.

Examples:

- Many subjects will feel a violation of privacy if they receive a letter asking them to participate in a study because they have _____ medical condition, when their name, contact information, and medical condition were drawn from medical records without their consent. Example: the IRB expects that "cold call" recruitment letters will inform the subject about how their information was obtained.
- Recruiting subjects immediately prior to a sensitive or invasive procedures (e.g., in an outpatient surgery waiting room) will feel like an invasion of privacy to some individuals.
- Asking subjects about sensitive topics (e.g. details about sexual behavior) may feel like an invasion of privacy to some individuals.

At all study sites providers meet with clients in a private room when they initiate PrEP. We will perform screening and consent in these offices or another private location at UW or with a community partner. We will encourage participants to answer the survey in a private setting. The peer will encourage participants to meet with them in private settings. This may not always be possible if the peer is accompanying the participant to the pharmacy, for example, but the peer will only engage in activities that the participant requests, and will ensure that privacy is protected as much as possible.

For the end-of-study interviews done in-person they will be done in a private setting. For interviews done via phone or Zoom, the interviewer will be in a private setting and will encourage the participant to also be in a private setting.

Interviews done in-person will be done in a private setting. For interviews done via phone or a HIPAA compliant Zoom account, the interviewer will be in a private setting and will encourage the participant to also be in a private setting.

9.2 Identification of individuals in publications and presentations. Do you plan to use potentially identifiable information about subjects in publications and presentations, or is it possible that individual identities could be inferred from what you plan to publish or present?

No

Yes → If yes, will you obtain subject consent for this use?

Yes

→ If no, describe the steps you will take to protect subjects (or small groups of subjects) from being identifiable.

9.3 State mandatory reporting. Each state has reporting laws that require some types of individuals to report some kinds of abuse, and medical conditions that are under public health surveillance. These include:

- Child abuse
- Abuse, abandonment, neglect, or financial exploitation of a vulnerable adult
- Sexual assault
- Serious physical assault
- Medical conditions subject to mandatory reporting (notification) for public health surveillance

Are you or a member of your research team likely to learn of any of the above events or circumstances while conducting your research **AND** feel obligated to report it to state authorities?

No

Yes → If yes, the UW IRB expects you to inform subjects of this possibility in the consent form or during the consent process, unless you provide a rationale for not doing so:

9.4 Retention of identifiers and data. Check the box below to indicate your assurance that you will not destroy any identifiers (or links between identifiers and data/specimens) and data that are part of your research records until after the end of the applicable records retention requirements (e.g. Washington State; funding agency or sponsor; Food and Drug Administration) for your research. If you think it is important for your specific study to say something about destruction of identifiers (or links to identifiers) in your consent form, state something like “the link between your identifier and the research data will be destroyed after the records retention period required by state and/or federal law.”

This question can be left blank for conversion applications (existing paper applications that are being “converted” into a Zipline application.)

See the “Research Data” sections of the following website for UW Records management for the Washington State research records retention schedules that apply in general to the UW (not involving UW Medicine data):

<http://f2.washington.edu/fm/recmgt/gs/research?title=R>

See the “Research Data and Records” information in Section 8 of this document for the retention schedules for UW Medicine Records: <http://www.uwmedicine.org/about/Documents/UWM-Records-Retention-Schedule-v1.6.pdf>

Confirm

9.5 Certificates of Confidentiality. Are you planning to obtain a federal Certificate of Confidentiality for your research data? *NOTE: Answer “No” if your study is NIH funded, because all NIH-funded studies automatically have a Certificate.*

No

Yes

9.6 Data and specimen security protections. Identify your data classifications and the security protections you will provide, referring to the [ZIPLINE GUIDANCE: Data and Security Protections](#) for the minimum requirements for each data classification level. **You cannot answer this question without reading this document. Data security protections should not conflict with records retention requirements.**

a. Which level of protections will you apply to your data and specimens? If you will use more than one level, describe which level will apply to which data and which specimens.

Since this study will enroll people who use meth, the data collected is extremely sensitive (level 5), since it regards illegal activity.

b. Use this space to provide additional information, details, or to describe protections that do not fit into one of the levels. If there are any protections within the level listed in 9.6.a which you will *not* follow, list those here.

When participants enroll in the study, the clinical sites will share the participants identifying information with the UW study team (name, contact information, etc.). For all participants this information exist in two locations: 1) the identifying folder in the locked cabinet in the PI's office will have the study code on it and 2) in a password protected file that is stored securely in a locked file cabinet in the PI's office. We will open a de-identified chart and use a code, which will be linked to the participant's identifying information. This link will be password protected and stored on a secure server at UW with limited access. We will collect a HIPAA Authorization and ROI at study entry to obtain clinical records and will ensure that these records are stored securely at UW. Self-reported meth use on the online surveys will be stored with REDCap, a secure HIPAA-compliant platform. We will send a unique survey link to each participant so that we can track who has completed the surveys without them needing to enter any identifying information. Dried blood spot specimens will be labeled with a name at the point of collection since they will be done at the clinic, but once transferred to the research team will be relabeled with the participants study code, so no identifying data will be on stored specimens.

For participants in the peer navigation group, we will also describe the risks associated with unsecured communication in the consent form. The peer will communicate with the participant based on their preferences. The peer will also have an encrypted, HIPAA-compliant app option that they can use to correspond with participants who wish to use the same app for communication. Participants in the peer navigation group will be encouraged to use this HIPAA-compliant app, and the peer will aid them in downloading it and using it as needed.

For specific types of study data, we will not be able to separate it from personal identifiers. This includes the data related to correspondence with participants assigned to receive peer support.

The correspondence the peer has with participants assigned to receive peer support will also link study data and personal identifiers. The method of and type of correspondence will be in response to the needs and requests of the participant. We anticipate that the peer and participant will correspond by email, text, and phone. We will store the peer and participant's correspondence, which will have identifiers (e.g. name, phone number, email address) in order to characterize the intervention to meet study aims (e.g. frequency of communication, method, general subject area). Study data will be downloaded from portable devices once every month.

Any fax communications that are sent for study purposes will be collected from the fax machine within 24 hours and stored per study protocol. The fax machine used for this study is a shared fax on a secure floor (13th) of the Ninth and Jefferson Building. Everyone who has access to the floor, and therefore the fax machine, is a UW employee with a badge. The fax machine is in a low traffic area, in the corner of the building near the administrative desks and is used regularly by a small number of UW employees for patient and participant communications. We check the fax machine as soon as possible if we are expecting a fax (e.g., a scheduled enrollment) and at least daily for unexpected faxes.

For the end-of-study interviews, we will encourage the participant not to use their name or the name of anyone else. If they do, we will omit those names during the transcription process and replace them with a de-identified label (e.g., "Interviewee", "Friend of Interviewee"). We will delete the audio recordings once the transcriptions have been reviewed against the audio recording for accuracy.

